4.1.2 SCIENTIFIC RATIONALE FOR STUDY DESIGN

The single-arm study design was chosen to evaluate the feasibility and acceptability of the NDURE intervention. Questionnaires to be used in the RCT assessing symptom burden, interpersonal support, knowledge, and self-efficacy will be collected pre- and post-intervention to assess the feasibility of data collection procedures and monitor completion rates. Post-intervention, patients will complete validated measures of PN acceptability. Qualitative work with patients and providers will help refine NDURE. Our interdisciplinary team will consult with our scientific advisory board and community advocacy group to interpret the data about the feasibility and acceptability of NDURE to refine recruitment, retention, and the content, format, timing, and delivery of NDURE for the planned RCT. We considered other study designs that involve randomization. Although such a study design would allow us to evaluate feasibility of enrollment when there is a control group option (and thus reasons for study decline), it would dilute the sample size thereby minimizing the amount of information gained about feasibility of accrual to the intervention necessary before proceeding to the RCT. In addition, since the control group in the RCT is usual care, randomizing patients to usual in the feasibility and acceptability study would not add useful information about the acceptability of the control to the control group beyond what is already known from recent clinical experience in this setting.

4.1.3 END-OF-STUDY DEFINITION

The end of the study is defined relative to completion of the 3-month follow-up assessment shown in the Schedule of Activities (SoA), **Section 1.3**.

4.2 RCT OF NDURE VERSUS USUAL CARE

4.2.1 OVERALL DESIGN

We will conduct a single-site, non-blinded, parallel-group, RCT of NDURE versus usual care for the management of delays and racial disparities starting PORT in adults with surgically-managed, locally advanced HNSCC. The study is designed to test the following hypotheses: 1) NDURE will result in a lower rate of delayed PORT relative to usual care (primary objective) and 2) NDURE will result in a smaller difference in PORT delay between AA and whites relative to usual care (secondary objective). The statistical plan for this between-group design analyzes the superiority of NDURE relative to usual care, although our power analysis is calculated with $\alpha = 0.1$ and $1 - \beta = 0.8$ based on the desire to emphasize power over type I error at this early stage of development (single-site pilot RCT) to ensure follow-up on promising interventions.

Upon enrollment and completion of the baseline assessments, patients will be randomized 1:1 to NDURE or usual care using a permuted block randomization method, with randomly selected block sizes of 2 or 4. Randomization, which will occur at the individual patient level, will be stratified with a 1:1 allocation ratio with strata defined by race (white, AA) and location of radiation facility (MUSC, non-MUSC) because of the known association of these variables with PORT delay^{6,33}. Furthermore, to facilitate evaluation of PORT delay rates in racial subgroups, we will oversample AAs for a final sample size of 50 white and 25 AA patients in each arm (see details in **Section 9.4.6, Sub-Group Analyses**). Given the impossibility of delivering the NDURE intervention in a non-blinded fashion, allocation concealment will be non-blinded. The study statistician ([name]) will generate the randomization schema and

randomization list. The study coordinator will implement the randomization. Randomization errors will be handled as per the modified intention-to-treat (ITT) population for the efficacy analysis.

NDURE is a theory-based, multi-level PN intervention consisting of three sessions of manualized PN with multiple intervention components that target system- (care coordination), interpersonal- (social support), and individual- (HBM; perceived susceptibility, severity, barriers, self-efficacy) level health behavior theoretical constructs to reduce barriers to care, increase HNSCC care delivery, and improve clinical outcomes (timely, equitable PORT). NDURE will be delivered from surgical consultation to PORT initiation (~3 months). The three NDURE navigation sessions, which are expected to take 30-60 minutes each, will coincide with the presurgical consult, hospital discharge, and 1st postoperative clinic visit, time points chosen to facilitate case identification and coordination across key care transitions.

In the RCT, NDURE will be compared with usual care. Usual care consists of clinic-based, provider-led discussion about the referrals needed to start PORT. Usual care was selected as the appropriate comparison group because it is the current standard for the population under study. Limitations of comparing NDURE to usual care (instead of active control) include the potential that improvements seen with NDURE (relative to usual care) are due to nonspecific effects. However, we are collecting data about the potential behavioral mechanisms underlying NDURE, which helps to limit the concern about non-specific effects of the NDURE intervention. In addition, given the pilot nature of this study, the goal is to achieve superior outcomes for patients over and above standard of care; therefore, usual care is a reasonable and appropriate comparison condition³⁴. In the future, as we continue to assess and establish the efficacy of NDURE in larger trials, we will explore the ‘active ingredients’ relative to active control to better isolate the mechanisms underlying its efficacy.

Because of the pilot nature of the study, refining the NDURE intervention is critical to ensure that NDURE is optimally developed and delivered prior to future definitive efficacy testing. As such, we will conduct qualitative, semi-structured interviews on n=25 (20% of the subjects enrolled in NDURE [n=15] and n=10 providers) to assess perceived barriers and facilitators to NDURE delivery, qualitatively assess mechanisms of change, and optimize NDURE for future research.

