2.2.2 DELAYS IN CANCER CARE DELIVERY FOR PATIENTS WITH HNSCC

Delays starting PORT contribute to high mortality in HNSCC and racial disparities in survival. Delays in cancer care delivery are a key driver of mortality for HNSCC patients¹⁴ and a source of racial disparities in survival for AAs³. The critical time period for HNSCC patients is the time from surgery to the start of PORT^{8,15}, the only aspect of timely HNSCC care incorporated in National Comprehensive Cancer Network (NCCN) Guidelines (\leq 6 weeks after surgery)⁵. Delays starting PORT are associated with increased recurrence and decreased survival^{7,16,17}. The 11% improved 5-year survival seen with timely PORT⁷ is large, comparable in magnitude to the benefit seen from adding Cisplatin to PORT in landmark HNSCC trials^{18,19}. Unfortunately, delays starting PORT affect 56% of HNSCC patients⁶. Delays starting PORT also disproportionately affect AAs, who are 31% more likely to experience delays than whites after

adjusting for insurance, income, education, and stage⁶. The high rate of delayed PORT among AA HNSCC patients is a source of preventable mortality and contributes to racial disparities in survival⁷.

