9 STATISTICAL CONSIDERATIONS

9.1 STATISTICAL HYPOTHESES

- Primary Endpoint:

PORT Delay

We hypothesize that, compared with patients who receive usual care, patients who receive NDURE will have a decreased rate of PORT delay (initiation of PORT > 6 weeks after surgery). Alternatively, our null hypothesis is that there will be no difference in the rate of PORT delay between NDURE and usual care.

The preliminary efficacy analysis will be calculated for the primary endpoint over the 6 week time period from the date of definitive surgical resection of the primary tumor.

- Secondary Endpoints:

PORT Delay

We hypothesize that, compared with usual care, NDURE will result in a smaller difference in the rate of PORT delay (initiation of PORT > 6 weeks after surgery) between AA and white patients. Alternatively, our null hypothesis is that there will be no difference in the rate of PORT delay between AA and white patients between NDURE and usual care.

The preliminary efficacy analysis will be calculated for the primary endpoint over the 6 week time period from the date of definitive surgical resection of the primary tumor.

TTP

We hypothesize that, compared with patients who receive usual care, patients who receive NDURE will have a shorter median TTP (time, in days, between the date of definitive surgical resection to the initiation of PORT). Alternatively, our null hypothesis is that there will be no difference in median TTP between NDURE and usual care.

TTP

We hypothesize that, compared with usual care, NDURE will result in a smaller difference in the median TTP between AA and white patients. Alternatively, our null hypothesis is that there will be no difference in the median TTP between AA and white patients between NDURE and usual care.

NDURE Accrual

We hypothesize that at least 60% of eligible subjects for the NDURE study will accrue to the study. Alternatively, our null hypothesis is that less than 60% of eligible subjects for the NDURE study will accrue to the study.

The preliminary feasibility analysis will be calculated for the secondary endpoint using the first 25 patients eligible to accrue to the study, which is expected to occur over 4 months.

NDURE Completion

We hypothesize that at least 85% of subjects who enroll in the NDURE study (at least 13 of 15 subjects) will complete all 3 NDURE sessions. Alternatively, our null hypothesis is that less than 13 of the 15 subjects who enroll in the NDURE study will complete all 3 NDURE sessions.

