9.2.2 RCT OF NDURE VERSUS USUAL CARE

Power and sample size calculations were performed using PASS v08.0.13, “Inequality Tests for Two Independent Proportions.” The primary endpoint for this pilot RCT is the rate of PORT delay, defined as starting PORT > 6 weeks after surgery. Our primary objective is to compare PORT delay rates between the NDURE and usual care arms. We hypothesize that, compared with patients who receive usual care, patients who receive NDURE will have a decreased rate of PORT delay (initiation of PORT > 6 weeks after surgery). Alternatively, our null hypothesis is that there will be no difference in the rate of PORT delay between NDURE and usual care. We assume the rate of PORT delay in the usual care arm will be 45%³³ and target an absolute reduction in PORT delay of 20% (rate of PORT delay in the NDURE arm = 25%)²⁴. This effect size is clinically significant and realistic given results in similar (non-randomized) interventions²⁴. Seventy-five patients in each arm yields 83% power to detect a 20% reduction in PORT delay (45% versus 25%) based on a two-sided Mantel-Haenszel test of two independent proportions assuming a two-sided $\alpha = 0.1$. Our choice of the Mantel-Haenszel test to compare proportions is based on the trial’s stratified design. Our selection of $\alpha = 0.1$ and $1 - \beta = 0.8$ is based on the desire to emphasize power over type I error at this early stage of development (single-site pilot RCT) to ensure follow-up on promising interventions. We therefore consider our RCT to be appropriately and rigorously designed to detect a clinically meaningful reduction in PORT delay. In order to have 150 patients eligible for the

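### The racial-disparity hypothesis is worded only as a smaller AA-white difference, Section 9.4 never estimates the between-arm change in disparity, and the answer depends on the scale chosen

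*Combined protocol and SAP*

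**What the plan says.** Section 4.2.1 gives the secondary hypothesis of the RCT as "NDURE will result in a smaller difference in PORT delay between AA and whites relative to usual care". Section 9.1 states it for the binary endpoint as "NDURE will result in a smaller difference in the rate of PORT delay" between AA and white patients, and for time to PORT as "NDURE will result in a smaller difference in the median TTP between AA and white patients". Each version speaks of a difference. None names a ratio measure or labels the scale as absolute or relative.

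The problem that motivates the hypothesis is put mainly in relative form. Section 2.2.2 refers to "AAs, who are 31% more likely to experience delays than whites", a covariate-adjusted figure, and Sections 2.1 and 2.2.5 use the same 31%.

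For the analysis:
- Section 9.4.2.2 plans delay percentages with 95% CIs for each race within each arm. Its one test is a Mantel-Haenszel comparison of the arms, with race and radiation facility as strata.
- Section 9.4.3.2 plans median time to PORT by race within arm, plus a stratified log-rank test and a Cox model that compare the arms.
- Section 4.2.1 sends the reader to Section 9.4.6 for details on the racial subgroups. Section 9.4.6 says only that race is handled as a secondary objective and not as a subset analysis.

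No between-arm race contrast, interaction estimate, decision rule or precision is given for the disparity hypothesis.

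**The concern.** When two groups start from different rates, a change in their difference and a change in their ratio are separate quantities, and they can move in different directions on the same data. The plan motivates the disparity on one scale and, on the natural reading of its hypothesis, judges it on the other. It then leaves the reader to work out the answer from four cell percentages.

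A smaller gap in the NDURE arm could be reported as reduced racial disparity although AA patients remain as much more likely to be delayed, in relative terms, as under usual care, or become more so. Section 2.2.5 rests part of the rationale on navigation working best in racial minority populations, and a smaller absolute gap cannot separate that premise from one proportional benefit shared by both races. Section 4.2.2 says the pilot is to inform a definitive phase III trial, so an ambiguous disparity result would carry forward.

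**Working it through.** **Inputs from the protocol.** Delay is 45% under usual care and 25% under NDURE, with 75 patients per arm and two-sided alpha 0.1 (Section 9.2.2). Each arm has 50 white and 25 AA patients (Section 4.2.1). AA patients are 31% more likely to be delayed (Section 2.2.2).

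**The plan's own figure.** The only stated power is 83% for the overall comparison.
- Null SE = √(2 × 0.35 × 0.65 / 75) = 0.0779.
- Alternative SE = √(0.45 × 0.55/75 + 0.25 × 0.75/75) = 0.0762.
- Power = Φ[(0.20 − 1.645 × 0.0779)/0.0762] = 82.7%.

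This reproduces. No corresponding figure exists for the disparity hypothesis.

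**Usual-care rates by race (assumed).** The documents give no race-specific rates for the RCT. I read 31% as a risk ratio and let the 2:1 mix average 45%. Then (2w + 1.31w)/3 = 0.45, so w = 1.35/3.31 = 40.8% for white patients and 1.31 × 40.8% = 53.4% for AA patients. The gap is 12.6 points and the ratio 1.31.

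**Three ways to reach 25% overall with the same effect in both races.**

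| Common effect | White | AA | Gap (points) | AA/white ratio | Fall, white | Fall, AA |
|---|---|---|---|---|---|---|
| Usual care | 40.8% | 53.4% | 12.6 | 1.31 | – | – |
| Risk ratio 0.25/0.45 = 0.556 | 22.7% | 29.7% | 7.0 | 1.31 | 18.1 | 23.7 |
| Odds ratio 0.402 | 21.7% | 31.6% | 9.9 | 1.46 | 19.1 | 21.8 |
| Equal 20-point fall | 20.8% | 33.4% | 12.6 | 1.61 | 20.0 | 20.0 |

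The gap falls 44% under a common risk ratio and 22% under a common odds ratio. It does not change under an equal absolute fall.

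**Sensitivity to the assumed baseline.** If 31% is read as an odds ratio, usual care is 42.8% v 49.5%, a gap of 6.7 points. A common risk ratio takes it to 3.7 (again 44% smaller) with the ratio unchanged at 1.16. For assumed baseline gaps of 10 to 25 points, a common risk ratio shrinks the gap by 4.4 to 11.1 points, and a common odds ratio shrinks it by 20 to 22% while the ratio rises. The pattern does not depend on the baseline.

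**Precision of the gap change.** I used unpooled variances under the common risk ratio.
- SE = √(0.534 × 0.466/25 + 0.408 × 0.592/50 + 0.297 × 0.703/25 + 0.227 × 0.773/50) = 0.163, about 16 points.
- The 95% CI half-width is 1.96 × 0.163 = 32 points.
- A change of (1.96 + 0.84) × 0.163 = 46 points would be needed for 80% power at two-sided 0.05, or about 41 points at 0.1.
- For the log ratio of risk ratios, the SE is the square root of the sum of (1 − p)/(np) over the four cells, which is √0.227 = 0.476. Its 95% CI runs a factor of exp(1.96 × 0.476) = 2.5 either side of the estimate.

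**How often the scales disagree.** I simulated trials with these cell sizes under the three effects in the table. The estimated gap is smaller in the NDURE arm while the estimated ratio is not in about 14% (risk ratio), 16% (odds ratio) and 17% (equal fall) of trials.

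**The case against.** The absolute scale is a legitimate choice, and the plan's own target effect is absolute (20 points). A reader might infer that the gap shrinks automatically whenever NDURE lowers delay equally in both races, so that reduced disparity could be concluded with no race-specific benefit. The documents do not support that, for three reasons.
- An equal 20-point fall leaves the gap unchanged. Shrinkage follows only from a common relative or odds effect.
- A smaller gap does require a larger absolute fall in AA patients (23.7 v 18.1 points under the common risk ratio), which is a real benefit on that scale.
- The plan has no rule by which reduced disparity is concluded. If a test were run, a common risk ratio would give a significant shrinkage in only about 4 to 10% of trials at two-sided 0.05, or 7 to 17% at 0.1, across the baselines considered.

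Nor does the second hypothesis simply restate the first, since overall delay can fall with the gap unchanged.

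It is also fair that the background is not purely relative: Section 2.2.5 gives timely-PORT rates of under 50% overall and under 40% in AA patients. The objective is secondary and preliminary, and the planned cell percentages would let anyone compute both measures.

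All of this stands, and it limits the point. It does not supply the missing between-arm estimate. Nor does it remove the exposure to a descriptive claim: under a common risk ratio the estimated gap is smaller in the NDURE arm in about 57 to 75% of trials, against 50% under an equal absolute fall.

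**Conclusion.** The concern holds as one of scale and of a missing estimand. The disparity hypothesis is worded as a difference, the background figure is a ratio, and Section 9.4 estimates the change in neither. With the protocol's overall rates, one uniform effect yields a gap of 7.0, 9.9 or 12.6 points and a ratio of 1.31, 1.46 or 1.61, depending on the scale on which it is uniform. A smaller absolute gap is therefore not evidence of a larger relative benefit in AA patients, and an unqualified statement that disparity was reduced would be ambiguous.

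The race-specific rates rest on two assumptions: that 31% is a risk ratio, and that it can be combined with the 45%, which comes from a different cited source. The scale dependence holds for every baseline tried. With an SE of about 16 points for the gap change, the trial can describe the change in disparity but can hardly test it.

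**What to change.** In Sections 9.1 and 9.4.2.2:
- State that the hypothesis concerns the absolute scale.
- Prespecify the between-arm change in disparity as two estimates, each with a CI: the difference between arms in AA-minus-white risk differences, and the ratio between arms of AA/white risk ratios.
- Say that if the two disagree, both will be reported and reduced disparity will not be claimed without qualification.
- State the expected precision (SE about 16 points for the gap change with 25 AA and 50 white patients per arm) and present the result as descriptive.

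I would not require both measures to move toward equality before a reduction is claimed. Such a rule has no error control, and both point estimates fall in about 49% of simulated trials under a common risk ratio. I would also not label a reduction seen only on the absolute scale as a mere by-product of lower overall delay, because it reflects a larger absolute fall in AA patients.

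The cost is a few lines of text, one or two more output lines and a more cautious disparity statement. No new data or patients are needed.

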4.2.2 SCIENTIFIC RATIONALE FOR STUDY DESIGN

We considered alternative study designs such as a single-arm pilot study with comparison to local and national historical control data. However, we consider the RCT a superior approach to a single-arm trial comparing to historical control³⁵ because the RCT will allow us to demonstrate and precisely measure the control group, thereby avoiding sample error and case-mix differences between the single-arm and historical control³⁶. As a result, the RCT design will provide us with more precise estimates of the effect size and sample size of the NDURE intervention relative to usual care in preparation for the definitive phase III RCT³⁷. Although methodological challenges (e.g. contamination)³⁸, will exist from running a single-site RCT (because providers will have patients in both NDURE and usual care concurrently), our group has experience successfully conducting single-site pilot RCTs^{39,40}. Other groups testing PN have similarly reported successful study completion and avoidance of significant contamination when studying PN in the single-arm setting¹⁰.

We also considered alternative comparison groups, including a form of active control against which to compare NDURE. Usual care is a more appropriate comparison group than active control because usual care represents the current standard for the management of this clinical scenario in population under study. Limitations of comparing NDURE to usual care (instead of active control) include the potential that improvements seen with NDURE (relative to usual care) are due to nonspecific effects instead of key ‘active ingredients’ within the NDURE intervention. However, a secondary objective of the trial is to

evaluate the preliminary behavioral mechanism of action of NDURE. As such, the data that we will analyze regarding underlying behavioral mechanisms will help to limit the concern about non-specific effects of the NDURE intervention. In addition, given the pilot nature of this trial, our goal is to achieve superior outcomes for patients over and above standard of care; therefore, usual care is a reasonable and appropriate comparison condition³⁴. In the future, as we continue to assess and establish the efficacy of NDURE in larger trials, we will explore the ‘active ingredients’ relative to active control to better isolate the mechanisms underlying its efficacy.

4.2.3 JUSTIFICATION FOR INTERVENTION

4.2.3.1 JUSTIFICATION FOR THE MODE OF DELIVERY

PN is a patient-centered intervention that addresses barriers to cancer care, thereby improving the delivery of timely, equitable cancer screening, decreasing racial differences in post-screening diagnostic resolution, and decreasing care fragmentation^{10,25-27}. Although technology-enhanced interventions are increasingly common to facilitate care coordination, PN at its heart is still a patient-centered intervention and is delivered in person via face to face interactions. Face to face interactions can unduly burden patients and result in decreased intervention adherence. In addition, face to face interactions are being minimized to promote patient and healthcare worker safety during the COVID-19 pandemic.

The preferred method for delivering NDURE is face to face. However, due to changes in healthcare delivery necessitated by COVID-19 pandemic, it is permissible for the NDURE navigator to use a telemedicine videoconferencing platform for NDURE sessions 1 or 3 (study visit 2 or 4). The number, frequency, and timing of intervention contacts (see details in **Section 4.2.3.2, Justification for Number, Frequency, and Timing of Intervention Contacts**) were carefully chosen to minimize potential concerns that may arise from face to face interactions. In addition, supplemental contact beyond the three prescribed sessions will occur with a frequency and modality (e.g. text message, email, etc.) dictated by patient and navigator need.

